7.3.2. Six Minute Walk Distance

Endpoint: Exercise capacity, as determined by 6MWD, will be assessed as defined in Section 7.2.1, *Computation of the Primary Endpoint*.

Changes in PAH medication use will be recorded on the *Initiation of New PAH Medications and Therapy* CRF page, and will be used to determine whether subjects had changes in their background PAH medications before and/or after the Week 24 visit (yes/no).

Analysis: Analyses analogous to those specified for the primary endpoint will be performed for longitudinal changes in the 6MWD at Week 48. See Section 7.2.2, *Primary Analysis of the Primary Endpoint*, for more details on the analyses. Data for this model will include all available data to Week 48. Additionally, the model will include a covariate to indicate changes in PAH therapeutic agents before and/or after the 24 week time point (yes/no). The interaction between this covariate and treatment will be included if significant (p-value<0.05). Spaghetti plots of the data will also be assessed to define any time trends that may need to be reflected in the model.

Additional models may be developed to assess the effect of other covariates.

7.3.3. Clinical Worsening

Endpoint: Assessment of time to clinical worsening, censored at 48 weeks, will be defined as first occurrence of the following: death, hospitalization for SSc-PAH, lung transplantation, atrial septostomy, addition of other PAH therapeutic agents, or worsening of 6MWD by > 20% and

an increase in functional class. The components of clinical worsening will be assessed as follows.

- a. Death: Date of death will be collected on the Post-Study Follow-Up/Week 104 Vital Status CRF page.
- b. Hospitalization for SSc-PAH: Date of hospitalization for SSc-PAH will be collected on the Serious Adverse Event CRF page and determined from SAEs that had seriousness criteria of “Required hospitalization or prolongation of existing hospitalization” and that were marked as being possibly, probably, or definitely related to worsening disease on the Adverse Events CRF page. Time to the event will be derived from the date that the AE became serious. If a subject has multiple hospitalizations for SSc-PAH, then the first date will be used.
 - i. A second clinical worsening endpoint will be similarly defined except that “hospitalizations for SSc-PAH” will be evaluated by a blinded review panel to exclude those events relating only to a subject’s SSc and not PAH.
- c. Lung transplantation: Date of lung transplant will be collected on the Initiation of New PAH Medications and Therapy CRF page.
- d. Atrial septostomy: Date of atrial septostomy will be collected on the Initiation of New PAH Medications and Therapy CRF page.
- e. Addition of other PAH therapeutic agents: Date of new medications or doses of PAH medications changed for the treatment of PAH will be collected on the Initiation of New PAH Medications and Therapy CRF page.
- f. Worsening of 6MWD by > 20% and an increase in functional class: The 6MWD and the NYHA Functional Class Assessment will be performed at Screening and Weeks 4, 12, 24, 36, and 48; they may also be performed at an unscheduled visit. Data for the 6MWD will be collected on the 6-Minute Walk Test CRF page and data on functional class will be collected on the NYHA Functional Class Assessment CRF. The first date at which the 6MWD has decreased by >20% from the Screening walk distance and the NYHA Functional Class Assessment has increased a class from Screening will be recorded. If a subject’s 6MWD decreased from Screening by more than 20% and a repeat 6MWD was performed, then the better of the two values will be used in the analysis. If a subject is NYHA Class IV at baseline, then only a decrease of 20% in the 6MWD will be required.

Time to clinical worsening will be defined as the first date that meets any of the above criteria and will be calculated in study days as: date of first event – date of randomization. If a subject does not experience a relevant event by Week 48 or if the date of death is after the 48 week follow-up period, then time to clinical worsening will equal the duration of follow-up in the main study for that subject. Appropriate censor variables will be defined to indicate whether the time-to variable represents an event time or a censor time.

Analysis: Time to clinical worsening and type of clinical worsening reached will be summarized by treatment group and overall. Kaplan-Meier curves, including 95% confidence intervals, will be created for each treatment arm and will be compared using the log-rank test. A Cox proportional hazards model may be fit to assess the effect of treatment on time to clinical worsening, if appropriate. Additional covariates may be added to the model as appropriate. Analyses will be run using the definition of hospitalization of SSc-PAH as defined in both point B and B.i above.

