6.5.4.13 Week 104 (Visit 17)

An assessment of vital status approximately two years post randomization will be conducted via telephone or review of public records or health registries (to which the subject has consented to share this data).

For subjects who completed their participation prior to the approval of protocol version 8.0, every possible effort to contact these subjects to consent them for this assessment should be made.

Assessments:

- Vital status
- Treatment Satisfaction assessment

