8.3.2. Deaths

Any death that occurs while a subject is active in the main study (up to Week 48) will be collected and reported as a SAE, and any death that occurs after main study completion will only be reported as a SAE if the subject is active in quarterly monitoring for B cells and if the cause of death is determined to be a Grade 3 or higher infection. Additionally, an assessment of vital status approximately two years post randomization will be conducted via telephone or

review of public records or health registries (to which the subject has consented to share this data). Any deaths discovered from this review will be recorded on the Post-Study Follow-Up/ Week 104 Vital Status CRF page.

Treatment-related mortality will be defined as death occurring after randomization and before Week 48, and possibly, probably, or definitely resulting from study treatment. Treatment-related mortality can only be assessed if a death was reported as a SAE; relationship to study treatment was not collected for deaths recorded on the Post-Study Follow-Up/ Week 104 Vital Status CRF page. As such, treatment-related mortality will be summarized at Week 48.

All-cause mortality, defined as any death occurring after randomization, will be summarized at Week 48 and Week 104.

In addition, time to all-cause mortality will be defined as the number of months post-randomization until death from any cause. If death does not occur during the post-randomization study period (up to Week 104), then time to all-cause mortality will be set equal to Week 104 or the day of the Week 104 vital status telephone call, whichever occurred first. Appropriate censor variables will be defined to indicate whether the time-to variables represent event times or a censor times. Kaplan-Meier survival curves from each treatment arm will be compared using the log-rank test.

Separate displays listing and summarizing death, including time to death and cause of death, will also be created

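### SAP 7.3.3(a) names the Week 104 page, not the SAE record, as the source of death dates for clinical worsening, so an on-study death could be censored instead of counted

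*SAP*

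**What the plan says.** SAP 7.3.3 defines time to clinical worsening as the time to the first of six components, with death listed first, censored at 48 weeks. Each component is tied to a CRF source. For death, item (a) says: "Date of death will be collected on the Post-Study Follow-Up/Week 104 Vital Status CRF page". No other source is given for it. Item (b), hospitalization for SSc-PAH, does name the Serious Adverse Event page.

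A subject with no relevant event by Week 48, or whose death falls after the 48-week period, is censored: "then time to clinical worsening will equal the duration of follow-up in the main study for that subject".

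SAP 8.3.2 describes two routes for deaths. For the main study: "Any death that occurs while a subject is active in the main study (up to Week 48) will be collected and reported" as an SAE. For the vital status check about two years after randomization: "Any deaths discovered from this review will be recorded on the" Week 104 page. The section treats the two as different data: "Treatment-related mortality can only be assessed if a death was reported as a SAE", because relatedness was not collected on the Week 104 page.

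**The concern.** The endpoint stops at Week 48, so the deaths it needs are those that SAP 8.3.2 routes to the SAE record. Item (a) points to the other record. A programmer working from 7.3.3 would read each item as the derivation source, and (a) does not send them to the SAE data. SAP Section 11 corrects the functional-class wording of this endpoint but leaves the death source as it is.

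If a death date is missed, the subject counts as having had no event, and follow-up in the main study ends on the day of death. The record becomes censoring at death. That censoring is informative: it removes events of the most serious component, and removes more of them from whichever arm has more deaths. The endpoint could then disagree with the Week 48 all-cause mortality summary in SAP 8.3.2.

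**Working it through.** The plan states no figure for this point, so there is none to reproduce. The check is a comparison of the texts.

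1. **Deaths the endpoint needs:** those from randomization to Week 48 (SAP 7.3.3).
2. **Where those deaths are recorded:** as SAEs (SAP 8.3.2).
3. **Where 7.3.3(a) looks:** the Week 104 page, which SAP 8.3.2 uses for deaths discovered by the two-year review.
4. **Does anything require an on-study death to be entered on both?** No such statement appears in either document. None excludes it either.
5. **Literal result for a subject who dies suddenly at Week 20, has an SAE report, no earlier worsening event and no entry on the Week 104 page:** no death date is found under (a), no other component is met, and the subject is censored at the end of main-study follow-up, which is Week 20.
6. **Intended result for the same subject:** an event at Week 20. Death is a listed component, the first qualifying date counts, and the only censoring clause specific to death covers deaths after the 48-week period.

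Steps 5 and 6 disagree, so the named source does not reliably deliver the defined endpoint.

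**Scale, for illustration only.** Protocol 1.1 cites one-year survival of 50-81% in SSc-PAH cohorts. With a constant hazard and 48 weeks = 336 days, deaths among 60 subjects = 60 × (1 − S^(336/365.25)):

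- S = 0.81: 60 × 0.176 = 10.6
- S = 0.50: 60 × 0.471 = 28.3

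These are background cohorts, not a forecast for this trial.

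To see how many events could depend on the source, assume 48-week mortality p of 5%, 10% or 18%, a 25% risk of non-fatal worsening, independent exponential hazards, and every on-study death absent from the Week 104 page. Apart from 18%, which is close to the S = 0.81 result, these inputs are assumptions and do not come from the documents. Then:

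- any event = 1 − (1 − p) × 0.75
- share of events that are deaths = ln(1 − p) / [ln(1 − p) + ln 0.75]
- first-event deaths = 60 × any event × share

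| p | Any event | Share | First-event deaths of 60 | Kaplan-Meier rate if all are censored |
|---|---|---|---|---|
| 5% | 28.8% | 0.051/0.339 = 15% | 2.6 | 25% |
| 10% | 32.5% | 0.105/0.393 = 27% | 5.2 | 25% |
| 18% | 38.5% | 0.198/0.486 = 41% | 9.4 | 25% |

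The share falls if non-fatal worsening is more common than 25%, if deaths tend to follow hospitalization or escalation of therapy, or if some deaths do appear on the Week 104 page.

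**The case against.** The best defence is that the plan's intent is clear and other provisions limit the damage.

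- **Intent.** SAP 7.3.3 treats deaths to Week 48 as events, and nothing says that deaths reported as SAEs are ignored. This stands, and it rules out reading the plan as a decision to censor on-study deaths. It does not mend the source: a clear intent with the wrong page named is still a derivation that can fail.
- **The page may hold these deaths anyway.** Protocol 3.1 plans vital status on all subjects, and the schedule footnote plans it for each subject, with public records or registries as fallback. The CRF completion instructions are not in the documents. This stands too, so the most that can be said is that deaths could be missed.
- **Other components catch some deaths.** A fatal hospitalization marked at least possibly related to worsening disease is an event under (b), and a death preceded by added PAH therapy is an event under (e). Item (b) would not catch a sudden out-of-hospital death, or a fatal infusion reaction or infection not attributed to worsening disease. Protocol 1.4 lists fatal infusion reactions and infections among the risks of rituximab.
- **Mortality is reported elsewhere.** SAP 8.3.2 summarizes all-cause mortality at Weeks 48 and 104, with Kaplan-Meier curves and a log-rank test, and SAP 8.2 tabulates AEs with an outcome of death. A reader might infer that a fatal treatment effect could go unseen in the trial; these analyses do not support that. The risk is confined to this endpoint.

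A reader might also infer from Protocol 6.5.4.13 that deaths before version 8.0 have no Week 104 entry, since it says: "For subjects who completed their participation prior to the approval of protocol version 8.0, every possible effort to contact these subjects" should be made. That text concerns subjects who completed participation, which Protocol 3.3.1 defines as completing Week 48. It does not describe subjects who died on study, so it cannot carry that inference.

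**Conclusion.** The mismatch is real and should be corrected. The source named in SAP 7.3.3(a) is not the one to which SAP 8.3.2 sends deaths up to Week 48. A literal derivation could censor an on-study death when two conditions hold together: the death is not also on the Week 104 page, and no other worsening event came first.

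A reader might infer that on-study deaths will be censored, or that 15-41% of events will be lost. The documents support neither. They do not say that on-study deaths are left off the Week 104 page. The percentages rest on every such death being missing, an assumed 25% non-fatal risk and independent hazards, so they are an upper bound under those assumptions. The actual size cannot be set from the documents and may be zero.

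The endpoint is secondary, and SAP 7.3 presents its p-values and intervals as descriptive. The primary analysis, the power statement and the type I error rate are not touched. The correction is still worth making, because this is a stated derivation rule that can give a wrong result for a component of the endpoint.

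**What to change.** Replace the sentence in SAP 7.3.3(a) with wording to this effect: the date of death is taken from the SAE/AE record for deaths during the main study and from the Post-Study Follow-Up/Week 104 Vital Status page otherwise; the actual date of death is used, not the onset date of the adverse event; discrepancies between the two sources are queried and reconciled before database lock.

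Specifying the actual date matters because 7.3.3(b) dates hospitalization from the day the event became serious, and that convention could otherwise be carried over to deaths.

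SAP 8.3.2 already describes both sources for mortality, so it needs only a check that its dates agree with those used here. The cost is one sentence in the SAP and one more dataset in the derivation, with no new data collection. If the change is made after database lock, Protocol 8.5.6 requires it to be documented in the clinical study report.

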3.2.2 Secondary Efficacy Endpoints

Secondary efficacy endpoints include the following clinical endpoints:

1. Change in PVR measured by right heart catheterization from baseline to 24 weeks after treatment initiation.
2. Exercise capacity, as determined by 6MWD, assessed longitudinally over the 48 weeks following treatment initiation.
3. Assessment of time to clinical worsening, censored at 48 weeks, defined as first occurrence of:
 - a. death,
 - b. hospitalization for SSc-PAH,
 - c. lung transplantation,
 - d. atrial septostomy,
 - e. addition of other PAH therapeutic agents, or
 - f. worsening of 6MWD by > 20% and a decrease in functional class.
4. Percentage of subjects who changed or added PAH therapeutic agents at 24 and 48 weeks.
5. Change in quality of life as determined by the SF-36 and disability index of the SHAQ from baseline to 24 and 48 weeks after treatment initiation.
6. Number of new digital ulcers assessed longitudinally over both the 24 and 48 weeks following treatment initiation.
7. Severity of Raynaud phenomenon, as measured by the VAS scale of the SHAQ, assessed longitudinally over both the 24 and 48 weeks following treatment initiation.
8. DLCO and oxygen saturation at rest on room air assessed longitudinally over both the 24 and 48 weeks following treatment initiation.
9. Change in PVR from baseline to 24 weeks after treatment initiation as a percentage of the baseline value.

Secondary efficacy endpoints also include the following mechanistic endpoints:

1. CD19 Studies
 - a. CD19+ B cells (absolute number and percentage of gated lymphocytes) at time of B cell depletion and longitudinally over the 48 weeks following treatment initiation, where B cell depletion is defined as < 5 CD19+ cells/ μ L.
 - b. Time to repopulation of CD19+ B cells, defined as the time point at which B cells recover to within 10% of baseline levels; if a baseline value is not available then recovery is defined as a B cell level of at least 90% of the lower limit of normal.

- c. Reconstitution pattern of B cell subpopulations assessed longitudinally over the 48 weeks following treatment initiation.
2. Level of anti-U1 RNP, anti-B23, anti-cardiolipin, anti-CENP-B, RF autoantibodies, and immunoglobulins, including IgG subclasses, measured by ELISA and assessed longitudinally over the 48 weeks following treatment initiation.

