5.7 Concurrent Medications and Therapy

5.7.1 Background PAH Therapy

From the time of study entry, subjects are to remain on background PAH medical therapy with either a single agent or a combination of prostanoid, endothelin receptor antagonist, PDE-5 inhibitor, and/or guanylate cyclase stimulators as per the entry criteria. Doses must remain stable through the week 24 primary endpoint visit.

Investigational prostanoids, endothelin receptor antagonists and PDE-5 inhibitors are permitted if the drugs are already in use for the treatment of PAH but are not currently licensed for this use by the FDA.

Permitted Dose modifications:

- Toxicity management for any of the four classes of drugs
- Increase in prostacyclin dose of up to 10% for worsening disease independent of route of administration.

Other PAH medications, such as diuretics and anti-coagulation, should be managed by the treating physician according to institutional practice. Changes in diuretics and anti-coagulants are permitted throughout the duration of the study.

Stabilization/clinical improvement in PAH should result in no change to background therapy for the duration of the subject's participation in the study.

If a change in medical (beyond the 10% increase in prostacyclin dose) or surgical therapy is necessary for the treatment of progressive PAH before the week 24 primary endpoint visit then the subject will complete an Early Endpoint visit (see Section 6.5.6) and procedures in Section 3.3.2.1, *Follow-up Requirements for All Treated Subjects* numbers 2 and 3 will be followed.

After the week 24 endpoint visit, the doses of background therapies for PAH may be increased and other agents may be added as needed to treat worsening PAH if the subject experiences any one of the following:

- a deterioration in functional class and a decrease in 6MWD by $> 20\%$,
or
- the development of signs and symptoms of clinical right heart failure, such as worsening edema, ascites, and/or weight gain,
or
- other objective data suggesting clinical deterioration, such as worsening cardiopulmonary hemodynamics as evidenced by a $\geq 20\%$ decrease in cardiac output, a $\geq 20\%$ increase in mPAP, or a $\geq 20\%$ increase in PVR.

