5.7.2.1 Corticosteroids

Concurrent therapy prednisone (or equivalent corticosteroid) at ≤ 10 mg daily is permitted.

- Corticosteroid doses may be adjusted with within the 0-10 mg daily range, as clinically indicated, as long as they are stable for 4 weeks prior to the weeks 24 and 48 endpoint assessments.
- Intra-articular corticosteroid injections may be administered.
- To accommodate the occasional use of extra corticosteroids by patients for reasons not associated with SSc, increases of up to 60 mg/day that are decreased back to the baseline dose within 2 weeks are permitted. Only 2 such increases are permitted during the study. Subjects must be back to baseline doses of corticosteroid by 4 weeks prior to the week 24 and week 48 visits.

5.8 Toxicity Management Plan for Concurrent Therapy:

If discontinuation of an agent is required due to toxicity, the study physician will exercise clinical judgment in terms of whether to prescribe another agent within the same therapeutic class, add an agent from another therapeutic class, or continue with other background therapies already in place.

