7.3.4. Addition of PAH medications

Endpoint: New medications or doses of PAH medications changed for the treatment of PAH will be collected on the Initiation of New PAH Medications and Therapy CRF page. Date of the

new or modified medication along with reason for the change will be collected for the first time a PAH medication is modified or added.

Indicator variables for new or modified PAH therapeutic agents will be derived for two time points: prior to Week 24 and after Week 24. Time to the addition or modification of PAH medications will be defined in study days as: date of the first time a PAH medication is modified or added – date of randomization.

Analysis: The number and proportion of subjects who changed or added PAH therapeutic agents prior to Week 24 and after Week 24 will be summarized by treatment group and overall, along with the reason for changes to the background PAH medications. Time (in days) to the addition or modification of PAH medications will also be summarized by treatment group and overall.

Kaplan-Meier curves, including 95% confidence intervals, will be created for each treatment arm and will be compared using the log-rank test.

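### SAP 7.3.3(e) lets dose changes made to treat PAH count as clinical worsening, although the protocol's component is the addition of a PAH agent, and SAP Section 11 does not declare it

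*SAP*

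**What the plan says.** Protocol 3.2.2, item 3, defines clinical worsening as the first of six events. Item 3e is "addition of other PAH therapeutic agents, or" and says nothing about doses. Item 4 in the same list is a different secondary endpoint: "Percentage of subjects who changed or added PAH therapeutic agents at 24 and 48 weeks".

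SAP 7.3.3 opens by restating the component as an addition. It then says "The components of clinical worsening will be assessed as follows", and item (e) reads "Addition of other PAH therapeutic agents: Date of new medications or doses of PAH medications changed for the treatment of PAH will be collected", naming the Initiation of New PAH Medications and Therapy CRF page. The event-time rule follows: "Time to clinical worsening will be defined as the first date that meets any of the above criteria".

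Among the permitted dose modifications, Protocol 5.7.1 lists "Increase in prostacyclin dose of up to 10% for worsening disease independent of route of administration". The same section allows both dose increases and added agents after Week 24, on stated signs of deterioration.

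SAP Section 11 has one entry for 7.3.3, correcting the direction of the functional-class change.

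**The concern.** The protocol treats changing a dose and adding a drug as different things, and gives the combined outcome its own endpoint. SAP 7.3.3(e) applies that combined outcome to a component which the protocol limits to additions. A programmer following the SAP would then date a small permitted prostacyclin increase as an event of the same standing as death or lung transplantation.

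Two things are at stake. First, the composite would not measure what the protocol defined, and any dose change for PAH by Week 48 would feed both it and the analysis in SAP 7.3.4. Second, the widening is undeclared. Protocol 8.5.6 requires major departures to be noted in the SAP, and the event definition of a time-to-event endpoint is reasonably regarded as one.

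**Working it through.** The documents state no event count, hazard ratio or power for this endpoint, so there is no planned figure to reproduce. The check is a comparison of texts, followed by an illustration on assumed rates.

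**Texts side by side**

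1. Definition: Protocol 3.2.2 item 3e and the lead sentence of SAP 7.3.3 both say addition only.
2. Assessment rule: SAP 7.3.3(e) says new drug or changed dose, limited to changes made to treat PAH.
3. Event date: the earliest qualifying date, with no filter on drug, size or reason. Item (b), hospitalization, by contrast carries a relatedness filter and a blinded-panel variant.
4. Source: SAP 7.3.4, the changed-or-added analysis, uses the same description and the same CRF page. Its heading also says addition while its content covers modification.
5. The permitted increase: Protocol 5.7.1 allows it for worsening disease, 5.6 exempts it from prohibited therapy, and it does not prompt an Early Endpoint Visit. Because it is given for PAH, it meets step 2.
6. After Week 24: 5.7.1 names dose increases and added agents separately. Both meet step 2; only the second meets item 3e.
7. Declaration: the numbered list in Section 11 does not contain the change.

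**Possible number affected (assumed rates)**

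Suppose 5% to 15% of subjects have a dose change as their first qualifying event: 60 × 0.05 = 3 and 60 × 0.15 = 9. These 3 to 9 subjects would be counted as worsened on a date that item 3e would not use. One subject is 1/30 = 3.3% of an arm.

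**Direction (assumed rates)**

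Assume constant hazards over 48 weeks and worsening under the protocol definition of 30% on placebo and 15% on rituximab. The cumulative hazards are −ln(0.70) = 0.3567 and −ln(0.85) = 0.1625, so HR = 0.1625/0.3567 = 0.456. Now add dose-change events.

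- Equal in both arms at 5%, −ln(0.95) = 0.0513: HR = 0.2138/0.4080 = 0.52.
- Equal at 10%, −ln(0.90) = 0.1054: HR = 0.2679/0.4620 = 0.58.
- Equal at 20%, −ln(0.80) = 0.2231: HR = 0.3857/0.5798 = 0.67.
- If rituximab reduces dose changes by the same ratio, 0.456, the composite HR stays at 0.456.
- In the extreme case of 10% on placebo and none on rituximab: HR = 0.1625/0.4620 = 0.35.

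The composite HR is a weighted average of the two component ratios, so its direction depends on the effect of treatment on dose changes, which the documents do not give.

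**The case against.** The strongest reply is that item (e) only names a data source. Its label still says addition, the text after it says what a CRF page collects, and items (a), (c) and (d) are written the same way. On that reading the label is the criterion and a dose change is not an event. This is possible but weaker: the list is introduced as the way the components are assessed, no filter is stated, and the same wording in 7.3.4 does define a changed-or-added outcome. Even on this reading, the SAP leaves the programmer to guess.

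A second reply stands in part. These increases are not noise. The prostacyclin increase is for worsening disease, and increases after Week 24 require deterioration, so a sponsor could reasonably want them in the composite. That is a reason to declare the choice, not to leave it implicit. The SAP will tabulate the type of worsening reached, and 7.3.4 will tabulate reasons for change, but no planned table splits component (e) into new agents and dose changes.

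Four stronger readings might be inferred, and the documents do not support them.

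- That every PAH dose change counts. The SAP limits it to changes made to treat PAH, so one made only for toxicity is arguably outside.
- That counting a replacement drug after toxicity departs from the protocol. Protocol 5.8 leaves the physician to judge "whether to prescribe another agent within the same therapeutic class, add an agent from another therapeutic class", but item 3e has no filter on reason, so such a drug fits the protocol's wording about as well as the SAP's.
- That a later true addition is lost, because the Initiation page captures only the first change. SAP 7.3.4 does say this: "new or modified medication along with reason for the change will be collected for the first time a PAH medication is modified or added". But SAP 9.1.2 has the Background PAH Medications CRF completed at each modification or addition, so the date is recoverable.
- That the hazard ratio must move toward 1. That needs an assumption such as similar dose-change rates in both arms, which is doubtful for increases tied to worsening.

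**Conclusion.** The point holds as a mismatch of definitions. As written, SAP 7.3.3(e) counts dose increases of existing agents given for PAH as clinical worsening; Protocol 3.2.2 item 3e and the SAP's own lead sentence count only additions; and Section 11 is silent. This rests on the text and needs no assumed rate.

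The effect on the result cannot be sized. The 3 to 9 subjects and the hazard ratios above are illustrations on rates that are not in the documents, and the direction of any shift is unknown. The analysis is secondary and exploratory, with descriptive p-values and no multiplicity control, and the primary 6MWD analysis is unaffected. It should be corrected, but it does not threaten the trial's main conclusion.

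**What to change.** In SAP 7.3.3(e), count only the start of a PAH agent the subject was not already taking. Where the first entry on the Initiation page is a dose change, take the date of any later addition from the Background PAH Medications CRF (SAP 9.1.2). Keep the changed-or-added definition for 7.3.4.

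If dose changes are meant to count, say so in 7.3.3, list it in Section 11, and report the composite under the protocol definition alongside. Either way, settle it before unblinding, because an event definition chosen afterwards is open to challenge.

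Excluding substitutions made for toxicity would be a new restriction that item 3e does not contain. Use it at most as a labelled sensitivity analysis.

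The cost is SAP wording and derivation code, possibly a small blinded medication review, and somewhat fewer composite events.
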